8.4.2 Hypoglycaemic episodes

Plasma glucose should always be measured and recorded when a hypoglycaemic episode is suspected.

All plasma glucose (PG) values:

- $\leq 3.9 \text{ mmol/L} (70 \text{ mg/dL}) \text{ or}$
- > 3.9 mmol/L (70 mg/dL) occurring in conjunction with hypoglycaemic symptoms

should be reported in the diary by the subject from Visit 2 to Visit 32 (FU2) and in the eCRF by the investigator according to the instructions below.

Upon onset of a hypoglycaemic episode the subject is recommended to measure PG every 15 minutes until the SMPG value is >3.9 mmol/L (70 mg/dL) and/or symptoms have been resolved in accordance to current guidelines. 34

A SMPG value ≤3.9 mmol/L (70 mg/dL) or hypoglycaemic symptoms must trigger a hypoglycaemic episode form to be completed by the subject. Repeated SMPG measurements and/or symptoms, occurring within a period of 60 minutes after onset on a hypoglycaemic episode, will by default be considered as one hypoglycaemic episode until a succeeding SMPG value is >3.9

 Protocol
 Date:
 23 February 2018
 Novo Nordisk

 Trial ID: NN1218-4113
 Version:
 4.0
 4.0

 UTN: U1111-1180-0636
 Status:
 Final
 Final

 EudraCT no.: 2016-000878-38
 Page:
 49 of 112
 49 of 112

mmol/L (70 mg/dL) and/or symptoms have been resolved and should be reported on one hypoglycaemic episode form. SMPG measurements ≤3.9 mmol/L (70 mg/dL) or hypoglycaemic symptoms after the 60 minutes period shall trigger the reporting of a new hypoglycaemia episode and prompt the subject to fill out a new hypoglycaemic episode form until a succeeding measurement is >3.9 mmol/L (70 mg/dL) and/or symptoms have been resolved.

In case of several low SMPG values within the 60 minutes interval, the lowest value is the one that will be reported as the SMPG value for the hypoglycaemic episode but the start time of the episode will remain as the time for the first SMPG value and/or symptom.

The record should include the following information:

- Start date and time of the hypoglycaemic episode
- The PG level before treating the episode (if available) and any follow up measurements. The lowest value measured during the hypoglycaemic episode will be reported as the PG value for the episode, the remaining values will be kept as source data in the diary.
- Whether the episode was symptomatic (Yes/No)
 A hypoglycaemic episode starting without symptoms should be updated to symptomatic if the subject experiences symptoms later during the episode.
- Whether the subject was able to treat him/herself
- If the severity of a hypoglycaemic episode aggravates, only one hypoglycaemic episode should be reported reflecting the most severe degree of hypoglycaemia. Date, time and dose of last bolus insulin administration prior to the episode
- Date, time and dose of last basal administration prior to the episode
- Date and time of last main meal (not including snacks) prior to the episode
- Whether the episode occurred in relation to physical activity
- Change in any concomitant illness
- Any sign of fever and/or other acute disease
- Whether the subject was asleep when the episode occurred
- If yes, whether the symptoms of the episode woke up the subject

The answer to the question: "Was the subject able to treat him/herself?" must be answered "No" for an episode requiring assistance of another person to actively administer carbohydrate, glucagon, or take other corrective actions. Plasma glucose concentrations may not be available during an event, but neurological recovery following the return of PG to normal is considered sufficient evidence that the event was induced by a low PG concentration. 34

Oral carbohydrates must not be given if the subject is unconscious.

 Protocol
 Date:
 23 February 2018
 Novo Nordisk

 Trial ID: NN1218-4113
 Version:
 4.0
 4.0

 UTN: U1111-1180-0636
 Status:
 Final
 Final

 EudraCT no.: 2016-000878-38
 Page:
 50 of 112
 50 of 112

If the question "Was the subject able to treat him/herself?" is answered "No", the following information should be recorded by the subject:

- Who assisted in the treatment of the hypoglycaemic episode (i.e. medical person or non-medical person)?
- Where the treatment was administered (in clinic/emergency room/hospital or other. If the subject was treated in clinic/emergency room/hospital, whether they were transported in an ambulance or not)
- Type of treatment provided by another person (i.e. oral carbohydrates, glucagon, IV glucose or other)
- Were symptoms alleviated after administration of treatment?
- Factors contributing to the episode (i.e. physical activity, missed meal, diet change, medication error (i.e. overdose, mix-up between products, incorrect use of device), miscalculation of dose of antidiabetic medication, other factors not listed or unknown)
- Did the subject experience seizure?
- Was the subject unconscious/comatose?
- Did the subject experience any of the following symptoms $\frac{35}{2}$ (layman term used in the diary is specified in brackets if different from the protocol term)?
- Autonomic: sweating, trembling, hunger or palpitations (rapid or irregular heart beat)
- Neuroglycopenic: confusion, drowsiness, speech difficulty, visual disturbances, odd behaviour, impaired balance or incoordination (reduced ability to coordinate movement)
- General malaise: headache or malaise (feeling discomfort/unease)
- Other symptoms

The investigator must review the diary for low SMPG values not reported as hypoglycaemic episodes. The subject must be questioned whether any of the low values were severe, i.e. whether the subject was able to self-treat or not. If the subject was not able to self-treat, it has to be reported as a severe hypoglycaemic episode. Low SMPG values for non-severe hypoglycaemic episodes not having a hypoglycaemic episode form completed within 7 days since the SMPG measurement should be reported on a hypoglycaemic episode form with as much information as possible. Novo Nordisk will not query for additional data except for the start date, SMPG value and whether the subject was able to self-treat due to decreased validity of such data. 36, 37

The subject must be re-trained in how to report hypoglycaemic episodes if the investigator identifies low SMPG values not reported as hypoglycaemic episodes.

If the hypoglycaemic episode fulfils the criteria for an SAE then an AE form and a safety information form (SIF) must also be filled in the eCRF, see Section 12. One AE-form and SIF can cover several hypoglycaemic episode forms if the subject has not recovered between the episodes.

Page:

51 of 112

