12.2 Reporting of adverse events

All events meeting the definition of an AE must be collected and reported. This includes events from the first trial-related activity after the subject has signed the informed consent until the end of the post-treatment follow-up period (FU2). For subjects discontinuing trial products prematurely this also includes events after the post-treatment follow-up period until the last contact (Visit 30). The events must be recorded in the applicable eCRF forms in a timely manner, see timelines below and Figure 12–1.

During each contact with the trial site staff, the subject must be asked about AEs and technical complaints, for example by asking: "Have you experienced any problems since the last contact?"

All AEs, either observed by the investigator or subject, must be reported by the investigator and evaluated.

All AEs must be recorded by the investigator on an AE form. The investigator should report the diagnosis, if available. If no diagnosis is available, the investigator should record each sign and symptom as individual AEs using separate AE forms.

For SAEs, a safety information form must be completed in addition to the AE form. If several symptoms or diagnoses occur as part of the same clinical picture, one safety information form can be used to describe all the SAEs.

Protocol		Date:	23 February 2018	Novo Nordisk
Trial ID: NN1218-4113	CONFIDENTIAL	Version:	4.0	
UTN: U1111-1180-0636	CONFIDENTIAL	Status:	Final	
EudraCT no.: 2016-000878-38		Page:	67 of 112	

For all non-serious AEs, the applicable forms should be signed when the event is resolved or at the end of the trial at the latest.

Timelines for initial reporting of AEs:

[figure not shown]
The investigator must complete the following forms in the eCRF within the specified timelines:

• **SAEs:** The AE form **within 24 hours** and the safety information form **within 5 calendar** days of the investigator's first knowledge of the SAE. Both forms must be signed within 7 calendar days from the date the information was entered in the eCRF.

For SAEs requiring reporting on a specific event form: In addition to the above the specific event form within **14 calendar days** from the investigator's first knowledge of the AE.

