Hypoglycaemic episodes are classified according to the Novo Nordisk classification of hypoglycaemia (see Figure 17–1) and the ADA classification of hypoglycaemia (see Figure 17–2).

[figure not shown]
Novo Nordisk classification of hypoglycaemia

In normal physiology, symptoms of hypoglycaemia occur below a PG level of 3.1 mmol/L (56 mg/dL). Therefore, Novo Nordisk has included hypoglycaemia with PG levels below this cut-off point in the definition of BG confirmed hypoglycaemia.

Novo Nordisk uses the following classification (see Figure 17–1) in addition to the ADA classification:

Protocol		Date:	23 February 2018	Novo Nordisk
Trial ID: NN1218-4113	CONFIDENTIAL	Version:	4.0	
UTN: U1111-1180-0636	CONFIDENTIAL	Status:	Final	
EudraCT no.: 2016-000878-38		Page:	93 of 112	

- Severe hypoglycaemia according to the ADA classification. 34
- Severe or BG confirmed hypoglycaemia: An episode that is severe according to the ADA classification 34 or BG confirmed by a PG value <3.1 mmol/L (56 mg/dL) with or without symptoms consistent with hypoglycaemia.

Note: Glucose measurements are performed with capillary blood calibrated to plasma equivalent glucose values

BG: blood glucose PG: plasma glucose SMPG: Self-measured plasma glucose

Figure 17-1 Novo Nordisk classification of hypoglycaemia

Protocol
Trial ID: NN1218-4113
UTN: U1111-1180-0636

Date: 23 February 2018 | Novo Nordisk
Version: 4.0
Status: Final

[figure not shown]
Page:

94 of 112

ADA classification ³⁴ of hypoglycaemia

EudraCT no.: 2016-000878-38

- Severe hypoglycaemia: An episode requiring assistance of another person to actively administer carbohydrate, glucagon, or take other corrective actions. Plasma glucose concentrations may not be available during an event, but neurological recovery following the return of PG to normal is considered sufficient evidence that the event was induced by a low PG concentration.
- Asymptomatic hypoglycaemia: An episode not accompanied by typical symptoms of hypoglycaemia, but with a measured PG concentration ≤ 3.9 mmol/L (70 mg/dL).
- Documented symptomatic hypoglycaemia: An episode during which typical symptoms of hypoglycaemia are accompanied by a measured PG concentration ≤ 3.9 mmol/L (70 mg/dL).
- Pseudo-hypoglycaemia: An episode during which the person with diabetes reports any of the typical symptoms of hypoglycaemia with a measured PG concentration > 3.9 mmol/L (70 mg/dL) but approaching that level.

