Treatment emergent hypoglycaemic episodes are presented in terms of the number of subjects with at least one event (N), the percentage of subjects with at least one event (%), the number of events (E) and the event rate per 100 years of exposure (R). Separate summaries are made by severity considering all episodes, nocturnal and daytime episodes using Novo Nordisk and ADA classified episodes. All episodes will also be summarised by category, including summaries in relation to time since start of meal, as occurring within the following time intervals:

- During first 1, 2, and 4 hours after start of meal
- Between 1 (exclusive) to 2 hours (inclusive) after start of meal
- Between 2 (exclusive) to 3 hours (inclusive) after start of meal
- Between 3 (exclusive) to 4 hours (inclusive) after start of meal
- Between 2 (exclusive) to 4 hours (inclusive) after start of meal

The number of treatment emergent severe or BG confirmed hypoglycaemic episodes (all, daytime, nocturnal, 1 hour, 2 hours, 4 hours, 1 (exclusive) to 2 hours (inclusive), 2 (exclusive) to 3 hours (inclusive), 3 (exclusive) to 4 hours (inclusive), and 2 (exclusive) to 4 hours (inclusive) after start of the meal) will be analysed based on the FAS using a negative binomial regression model with a log-link function and the logarithm of the time period in which a hypoglycaemic episode is considered

Statistical Analysis Plan		Date:	12 February 2019	Novo Nordisk
Trial ID: NN1218-4113	CONFIDENTIAL	Version:	2.0	
UTN: U1111-1180-0636		Status:	Final	
EudraCT No.: 2016-000878-38		Page:	25 of 29	

treatment emergent as offset. The model will include treatment, region and metformin use at baseline (Yes/No) as factors. To the extent where data allow, separate analysis will be performed for severe hypoglycaemic episodes (all).

Change from baseline in clinical evaluations 16 weeks after randomisation:

Physical examination

The physical examination parameters (head, ears, eyes, nose, throat, neck, respiratory system, cardiovascular system, gastrointestinal system incl. mouth, musculoskeletal system, central and peripheral nervous system, skin), and their change from baseline, will be summarised descriptively using the on-treatment period. All findings will be listed.

Vital signs

Vital signs include diastolic blood pressure, systolic blood pressure and pulse. The measurements will be summarised descriptively using the on-treatment period and both actual values as mean change and change from baseline.

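### The site's only severity-specific question about hypoglycaemia is limited to low diary glucose values, so a severe episode with neither a reading nor a completed form meets only general prompts

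*Protocol*

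**What the plan says.** Protocol v4.0 section 8.4.2 gives the site a back-check on the paper diary: "The investigator must review the diary for low SMPG values not reported as hypoglycaemic episodes". The severity question follows directly: "The subject must be questioned whether any of the low values were severe, i.e. whether the subject was able to self-treat or not". Re-training of the subject is triggered in the same way, when the investigator "identifies low SMPG values not reported as hypoglycaemic episodes".

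The same section does not require a reading for a severe episode: "Plasma glucose concentrations may not be available during an event, but neurological recovery following the return of PG to normal is considered sufficient evidence". Section 17.4.2.2 defines severe hypoglycaemia as "An episode requiring assistance of another person to actively administer carbohydrate, glucagon, or take other corrective actions", with no glucose threshold. SAP section 2.4.2.2 uses the same definition.

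Section 8.4.2 also sets out what the subject does. Either a low value or symptoms must lead to an episode form. The glucose field is filled in only where a value exists, and the form asks whether the subject could self-treat. If not, it asks who helped, where and how.

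At every contact, section 12.2 requires a question about adverse events and technical complaints. Its example is open: "Have you experienced any problems since the last contact".

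**The concern.** The site's check for missed severe episodes relies on a low glucose value, which the definition of such an episode does not require. Someone who was asleep, confused or unconscious and was helped by a relative may not have measured glucose, and may not have completed a form afterwards. The protocol foresees these situations, since the form asks about sleep, seizure and unconsciousness. It records impaired awareness of hypoglycaemia at screening (section 8.2.3), and section 6.3 lists no exclusion for it, so the symptom trigger will be weak in some subjects.

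Severe episodes enter four places in the analysis:

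- the severe or BG confirmed episode counts, analysed by negative binomial regression;
- a separate analysis of all severe episodes, where data allow;
- the responder endpoint HbA1c below 7.0% with no severe episode;
- the responder endpoint overall 1-hour PPG at or below 7.8 mmol/L with no severe episode.

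In the two composites, a missed severe episode in a subject who meets the glycaemic target turns a non-responder into a responder. The separate severe analysis depends on there being enough events, so lost events may also affect whether it can be run.

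**Working it through.** The plan gives no figure to reproduce. The check is whether a severity-specific question reaches each kind of severe episode under v4.0.

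| Low reading in diary | Episode form completed | Is severity asked about? |
|---|---|---|
| Yes | No | Yes: the site's question in 8.4.2 |
| Yes | Yes | Yes: the self-treatment item on the form |
| No reading | Yes, because of symptoms | Yes: the same item on the form |
| No reading | No | No severity-specific question |

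Only the last row is open. The routes that still apply to it in v4.0 are:

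- section 12.2: the open adverse event question at each contact;
- section 8.6.3: diary review for adverse events and changes in health;
- section 8.7: the weekly check of diary completion, including hypoglycaemia reporting;
- section 8.1.8: hypoglycaemic episodes as a collection item at both follow-up contacts;
- section 8.1.11: correcting or adding missing hypoglycaemia data that are available elsewhere;
- section 12.1.2: serious adverse event reporting, if for example the subject was hospitalised.

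Each of these could bring the episode to light, but none asks whether someone had to help.

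The contact schedule matters. Of the 16 weekly contacts after randomisation, the flow chart shows 5 site visits (Visits 16, 18, 22, 26 and 30) and 16 − 5 = 11 phone contacts. The diary is handed in only at site visits (section 8.6.3), so at most contacts the site relies on what it asks.

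Effect on the comparison: let the true severe rates be λ₁ and λ₂, and let a fraction c of episodes be captured in both arms. The expected observed rates are cλ₁ and cλ₂. Their ratio is cλ₁ / cλ₂ = λ₁ / λ₂, so the rate ratio for severe episodes is unchanged in expectation. Each rate is understated by the fraction 1 − c, and precision falls because there are fewer events. In the composites, missed episodes raise the observed responder proportion in each arm. The documents give no value for c and no severe episode rate.

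**The case against.** The strongest reply is that v4.0 already captures most severe episodes without a reading. Symptoms alone must trigger a form, the glucose field may be empty, and self-treatment is asked about every time. This stands. A reader might infer that severe episodes without a reading are never specifically asked about, or that nothing beyond the open adverse event question could find them. The documents do not support either inference: the form asks, and sections 8.1.8, 8.1.11, 8.6.3 and 8.7 prescribe further review or collection of hypoglycaemia data.

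A second reply is that the consequence is limited. Severe episodes alone are not named as the main safety comparison. The planned model is for severe or BG confirmed episodes, where a glucose value below 3.1 mmol/L also qualifies, and the separate severe analysis is conditional on the data. Bolus treatment is double-blind, so a site has no reason to ask one arm more than the other. This stands too, and a reading of the gap as a bias in favour of one treatment is not supported.

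What the reply does not remove is the last row of the table. The general routes depend on the subject volunteering an assisted episode, or on the site happening to find it.

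**Conclusion.** The point holds in a limited form: a severe episode with neither a glucose reading nor a completed form meets no severity-specific question from the site. Some such episodes may be missing from the severe and severe or BG confirmed counts and from the two composite responder endpoints.

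The loss cannot be sized from the documents. A reader might try assumed rates. If 1% to 3% of 1072 subjects had a severe episode, that is 0.01 × 1072 ≈ 11 to 0.03 × 1072 ≈ 32 subjects; if 20% to 40% of them came to light only through a site prompt, about 2 to 13 subjects would be affected. Both rates are guesses. The second is not the share with neither reading nor form, the sum treats every one of those cases as missed despite the general routes, and it counts subjects rather than episodes. It should not be used as an estimate.

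The conclusion that the loss is likely similar in both arms rests on the blinding and on equal capture c. The expected harm is under-counting and lower precision. This is a cheap improvement to data collection, not a flaw that threatens the trial's conclusions.

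**What to change.** Keep the diary review for low values and add to section 8.4.2, in these or similar words:

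*At each visit or phone contact, ask the subject whether there has been, since the last contact, any suspected hypoglycaemic episode that he or she was not able to self-treat, as defined in this section, whether or not plasma glucose was measured. Report any such episode that meets the definition of severe hypoglycaemia on a hypoglycaemic episode form.*

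The question must stay tied to suspected hypoglycaemia and to the protocol's definition. Asking about any help from another person would bring in falls and other illness, and would inflate the endpoint.

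Protocol v2.0 section 8.4.2 had sites ask about severe episodes since the last visit when eDiary data were incomplete or incorrect. That text is superseded and its absence from v4.0 is not an error, but it shows that such a question is workable.

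The cost is one more question at contacts that already take place, a few more forms, a wording change and a note to sites.

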8.4.3 Eye examination

EudraCT no.: 2016-000878-38

Fundus photography/pharmacologically dilated fundoscopy must be performed by the investigator, a local ophthalmologist, or an optometrist according to local practice. The result of the fundus photography/pharmacologically dilated fundoscopy must be interpreted locally by the investigator. To document this, the investigator must sign and date the result page or write the interpretation in the subject's medical records.

The evaluation must follow the categories:

- Normal
- Abnormal
- Was the result clinically significant? (Yes/No)

Abnormal and clinically significant findings must be recorded as described in Section 8.4.

If a fundus photography/pharmacologically dilated fundoscopy has been performed within 90 days before Visit 2 and if the results are available at Visit 2, then the procedure does not need to be repeated. If performed before the subject consents to participate in the trial, it must also be stated in the subject's medical records that this procedure was not performed in relation to the trial.

The eye examination must be performed prior to administration of bolus trial insulin at Visit 14 (the results do not need to be available for randomisation). An eye examination performed within 14 days prior to randomisation is acceptable.

Eye examination obtained within 21 days prior to Visit 30 is acceptable if the result is available at the visit.

For subjects prematurely discontinued trial products: eye examination performed 21 days in advance of Visit 30A are acceptable if the results are available at the scheduled visits. However eye examination performed at Visit 14 cannot be accepted for the Visit 30A.

8.4.4 Electrocardiogram – 12 lead

An electrocardiogram (ECG)-12 lead must be performed locally. The ECG must be interpreted by the investigator, and documented by investigator signature and date on the ECG print-out or write the interpretation of the ECG in the subject's medical records.

The evaluation must follow the categories:

- Normal
- Abnormal
- Was the result clinically significant? (Yes/No)

Abnormal and clinically significant findings must be recorded as described in Section 8.4

If an ECG-12 lead has already been performed within 21 days before screening (Visit 1), and if the results are available at the screening visit, the procedure does not need to be repeated. If performed before the subject consents to participate in the trial it must also be stated in the subject's medical records that this procedure was not performed in relation to the trial.

ECGs performed 21 days in advance of Visit 14 and Visit 30 are acceptable if the results are available at the scheduled visits.

For subjects prematurely discontinued trial products: ECGs performed 21 days in advance of Visit 30A are acceptable if the results are available at the scheduled visits. However ECGs performed at Visit 14 cannot be accepted for the Visit 30A.

